5.3. Secondary Analyses

5.3.1. Tumor Response

Tumor response includes the BOR, ORR, DCR (or CBR) and DOR. Tumor response endpoints will be summarized for the mITT population, ITT population, and randomized subjects with 4 or more prior lines of therapy. The analysis will be based on ICR scans per to RECIST v 1.1. Results based on investigator assessment will also be provided. A by subject listing of tumor response data will be provided.

5.3.1.1. Best Overall Response

BOR is defined as the best response designation recorded between randomization date and the date of objectively documented progression per RECIST 1.1 or the date of initiation of subsequent therapy or palliative local therapy, whichever occurs first. For subjects without documented progression or subsequent therapy or palliative local therapy, all available response designations will contribute to the BOR determination. For this study responses of CR or PR require confirmation by a subsequent assessment that is performed a minimum of 4 weeks or later from when the initial response is observed. Table 4 illustrates how CR or PR responses will be confirmed.

BOR will be summarized using counts and percentages by treatment group, this analysis will be based on subjects with measurable diseases with at least 1 post-randomization assessment.

First Time Point Response ^a	Second Time Point Response	Confirmed Response (Best Response) ^b
PD	No further evaluation	PD
NE	PD	PD
CR	PD	SD or PD ^c
PR	PD	SD or PD ^c
SD	PD	SD or PD ^c
CR	CR	CR
CR	NE ^a	SD or NE ^d
PR	CR	PR
PR	PR	PR

 Table 4:
 Confirmed Response Based on Subsequent Assessment

First Time Point Response ^a	Second Time Point Response	Confirmed Response (Best Response) ^b
PR	SD ^{ae}	SD
PR	NEª	SD or NE ^d
SD	CR	SD
SD	PR	SD
SD	SD	SD
SD	NE	SD or NE ^d
NE	CR	SD
NE	PR	SD
NE	SD	SD
NE	NE	NE

Abbreviations: CR, complete response; NE, not evaluable; PD, disease progression; PR, partial response; SD, stable disease.

^a Subsequent documentation of CR may provide confirmation of a previously identified CR for subjects where the second integrated response was NE. Subsequent documentation of PR may provide confirmation of a previously identified PR for subjects where the second integrated response was NE or SD. If the third TPR confirms the CR (or PR) then the Confirmed Response will be CR (or PR). For this study, only one (1) intervening NE is allowed between CRs/PRs. For example: CR NE CR = CR; PR NE PR = PR. Additionally, one (1) SD is allowed between PRs (e.g., PR SD PR = PR).

^b A Best Response of SD can only be made after the subject is on-study for a minimum of 35 days. If the subject is on study less than 35 days, any tumor assessment indicating stable disease before this time period will have a Best Response of NE unless PD is identified.

^c Best response will be SD if the first TPR is after 35 days on study. Otherwise, the best response will be PD.

^d Best response will be SD if the first TPR is after 35 days on study. Otherwise, the best response will be NE.

^e TPR is SD if the increase from the first to the second assessment does not qualify for PD.

5.3.1.2. Objective Response Rate (ORR)

Objective response is defined as achieving a confirmed BOR of CR or PR per RECIST 1.1. ORR is defined as the proportion of subjects with objective response. The proportion of subjects with ORR and corresponding two-sided exact Clopper Pearson binomial 95% CIs will be provided by treatment group for both the ICR-assessed scans and investigator-assessed scans. Additionally, the difference between treatment arms and Wald 95% CI for the difference will be provided.

5.3.1.3. Disease Control Rate (or) Clinical Benefit Rate.

For this study, disease control (or clinical benefit) is defined as achieving a confirmed BOR of CR, PR, or at least 3 months of SD. The proportion of subjects who achieve disease control and corresponding two-sided exact Clopper Pearson binomial 95% CI will be estimated for both the ICR and investigator assessments. In addition, the difference between the groups and Wald 95% CI for the difference will also be provided.

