BOR will be summarized by response category for each treatment group. ORR will be computed in each treatment group along with the exact 95% CI using Clopper-Pearson method. An estimate of the difference in ORRs and corresponding 95% CI will be calculated using Cochran-Mantel-Haenszel methodology and adjusted by the same stratification factors as in primary analysis of PFS.

For subjects with at least 4 prior lines of treatment, a sensitivity analysis will be performed to explore the efficacy for this population.

PK: PK of unesbulin, DTIC, and AIC will be analyzed using standard compartmental or noncompartmental analysis methods, as appropriate for the data. The impact of unesbulin on the PK of DTIC and AIC will be investigated.

Safety: The safety analysis will be performed for all treated subjects. Descriptive statistics of safety will be presented using National Cancer Institute (NCI) Common Terminology Criteria for Adverse Events Version 5.0 (CTCAE V5.0) by treatment group. All treatment-emergent AEs will be tabulated by system organ class and Medical Dictionary for Regulatory Affairs (MedDRA) preferred term. Laboratory abnormalities, including hematology and chemistry, will be summarized using worst grade per NCI CTCAE V5.0 criteria.

SCHEDULE OF ASSESSMENTS

Table 1:	Schedule of Study	Assessments and Procedures
----------	-------------------	----------------------------

Assessment	Screening								Cycle 2									С	ycle	3 +			EOT ^a	FUP ^a	sFUP ^a
Study Week		1			2		3		1			2		3		1			2		3				
Cycle Day	-28 to -1	1	2	5	8	11	15	18	1	2	5	8	11	15	18	1	2	5	8	11	15	18			
Time Window ^b	-	2	1	1	2	1	2	1	2	1	1	2	1	2	1	2	1	1	2	1	2	1	1	3	3
Informed consent	Х																								
Eligibility	Х																								
Medical history	Х																								
Con. meds ^c	Х											Throu	ghout	stud	y									Х	
Pathology review ^d	Х																								
Physical exam ^e	Х	Х							Х							Х							Х		
Height	Х																								
Weight ^f	Х	Х							Х							Х							Х		
Vital signs	Х	Х							Х							Х							Х		
ECOG PS	Х	Х							Х							Х							Х		
Adverse events	Х										٦	Throu	ghout	stud	у									Х	
Laboratory tests ^g	Х	Х			Х		Х		Х			Х		Х		Х			Х		Х		Х		
HIV, hepatitis	Х																								
serologies																									
Urine/serum	Х	X ^h							X ^h							X ^h									
pregnancy test ^h																									
Urinalysis	Х																						Х		
ECG (single) for	Х	Х							Х							Х							Х		

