8.3. Analysis Populations

Intent-to-treat (ITT) population: will include all randomized subjects. Subjects will be grouped based on the group they are randomized to. If a subject receives treatment in the group different from the one to which he/she was randomized, the subject's efficacy data will be analyzed "as randomized." The ITT population will be used as sensitivity analysis for all efficacy analysis.

Modified Intent-to-treat (mITT) population: will include randomized subjects with 3 or less line of therapy. The mITT population will be used in all the efficacy analysis, including analyses of the primary and secondary endpoints. Subjects will be grouped based on the group they are randomized to. If a subject receives treatment in the group different from the one to which he/she was randomized, the subject's efficacy data will be analyzed "as randomized."

Safety population: will include all subjects who received at least one dose of study drug (unesbulin/placebo or DTIC). If a subject receives treatment in the group different from the one to which he/she was randomized, the subject's safety data will be analyzed "as treated." The Safety population will be used in the statistical analyses for safety.

PK population: will include safety population subjects who have at least one plasma concentration of unesbulin, DTIC, or AIC.

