8.4.4. Analysis of Other Secondary Efficacy Endpoints

Other secondary efficacy endpoints include ORR, DCR or CBR, and DoR.

ORR is defined as the proportion of subjects who achieve a confirmed best response of CR or PR using RECIST 1.1 as per independent radiologist assessment. BOR is defined as the best response designation recorded between randomization date and the date of objectively documented progression per RECIST 1.1 or the date of initiation of subsequent therapy or palliative local therapy, whichever occurs first. For subjects without documented progression or subsequent therapy or palliative local therapy, all available response designations will contribute to the BOR determination.

DCR or CBR is defined as the proportion of subjects with BOR of CR, PR, or at least 3 months of SD.

DoR is defined as the time from the date of first confirmed response to the date of the first documented tumor progression (per RECIST 1.1) or death due to any cause, whichever occurs first. Subjects who neither progress nor die will be censored on the date of their last evaluable tumor assessment. Subjects who started any subsequent anticancer therapy without a prior reported progression will be censored at the last evaluable tumor assessment before or on the date of initiation of the subsequent anticancer therapy. DoR will be evaluated for responders only.

The same statistical models applied to the analysis of PFS will be applied to the analysis of OS (Section 8.4.2).

BOR will be summarized by response category for each treatment group. ORR will be computed in each treatment group along with the exact 95% CI using Clopper-Pearson method. An estimate of the difference in ORRs and corresponding 95% CI will be calculated using Cochran-Mantel-Haenszel methodology and adjusted by the same stratification factors as in primary analysis of PFS.

DCR will be analyzed the same way as ORR.

DoR in each treatment group will be estimated using KM product-limit method for subjects who achieve PR or CR. Median values along with two-sided 95% CI will be calculated.

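### SAP 5.3.1 swaps the protocol's stratified ORR and DCR differences for a Wald interval and narrows the BOR table, while SAP 3.7 declares no change to efficacy analyses

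*SAP*

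**What the plan says.** **Protocol.** Section 8.4.4 says the ORR difference and its CI will be "calculated using Cochran-Mantel-Haenszel methodology and adjusted by the same stratification factors as in primary analysis of PFS". The synopsis repeats this. Section 8.4.4 adds: "DCR will be analyzed the same way as ORR". It asks for BOR by response category and arm, with no restriction on who is counted. Section 8.3 sets the population: "The mITT population will be used in all the efficacy analysis, including analyses of the primary and secondary endpoints".

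**SAP.** Section 5.3.1.2 (ORR): "Additionally, the difference between treatment arms and Wald 95% CI for the difference will be provided". Section 5.3.1.3 (DCR): "In addition, the difference between the groups and Wald 95% CI for the difference will also be provided". Neither mentions CMH, strata or weights. For the BOR summary, section 5.3.1.1 says "this analysis will be based on subjects with measurable diseases with at least 1 post-randomization assessment". Section 3.7 declares that the protocol's efficacy analyses, secondary ones included, are unchanged; the only departures it lists are the dropped patient-reported outcome and biomarker analyses.

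**The concern.** Section 3.7 is where a reader looks to learn whether the reported analyses are those the protocol promised. Here it says they are, although the method for the between-arm ORR and DCR comparison has changed and the base of the BOR table has narrowed. SAP section 1 has the clinical study report document deviations from the SAP. An analysis run exactly as the SAP describes would not be one, so the change could go unreported.

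Within the SAP, the BOR table and the ORR table can also show different CR-plus-PR percentages for the same responders, with nothing to tell the reader why. What is at stake is accurate and consistent reporting.

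**Working it through.** The documents give no ORR or DCR rate, power or sample size, so there is no figure of the plan's own to reproduce. The check is a comparison of texts, followed by an illustration of size.

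**1. Method.** Protocol: CMH difference over three binary factors (prior lines 1 or >1, ECOG 0 or 1, uterine or nonuterine), hence 2 × 2 × 2 = 8 strata. SAP: a difference with a Wald CI. By contrast, SAP 5.1.1 sets out strata, planned versus actual, in detail for PFS. The per-arm Clopper-Pearson intervals agree between the documents.

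**2. Denominators.** SAP 5.3.1.2 says "ORR is defined as the proportion of subjects with objective response" without defining the subjects there, but other sections do. SAP 2.2 uses mITT for all efficacy analyses, 3.1 makes the analysis set the default denominator, 3.2.3 defines the ORR population as randomised subjects with 1 to 3 prior lines, and 5.3.1 summarises tumour response for mITT. The restriction in 5.3.1.1 applies to the BOR summary only. BOR and ORR therefore have different bases.

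**3. Size of the method change.** With stratum k holding n1k and n0k subjects and x1k and x0k responders:

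- Crude: d = p1 − p0, with CI d ± 1.96·√[p1(1−p1)/n1 + p0(1−p0)/n0].
- CMH: d = Σ wk(p1k − p0k) / Σ wk, with wk = n1k·n0k/(n1k + n0k) and the Sato variance.

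If every stratum is exactly 2:1, then n1k = 2·n0k and wk = 2·n0k/3. The weights are then proportional to stratum size in both arms, and the two point estimates coincide. Example with assumed responders 30/200 and 8/100 and exact 2:1 strata:

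- Crude: 15.0% − 8.0% = 7.0%; SE = √(0.15·0.85/200 + 0.08·0.92/100) = 0.0371; 95% CI −0.3 to 14.3.
- CMH: 7.0%; 95% CI −0.1 to 14.1.

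Actual strata will not be exactly 2:1. The next figures come from simulated trials under assumed conditions: permuted blocks of 6, eight near-equal strata, each factor with odds ratio 1.5 to 2, ORR about 15% v 5%, DCR about 49% v 30%. N = 300 is the plan; 200 and 150 are assumed sizes for a trial stopped early. Mean absolute gap between crude and CMH differences, in percentage points:

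| N | ORR | DCR |
|---|---|---|
| 300 | 0.10 to 0.13 | 0.19 to 0.26 |
| 200 | 0.17 to 0.21 | 0.31 to 0.41 |
| 150 | 0.26 to 0.30 | 0.45 to 0.58 |

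At N = 300 the mean CI width for ORR is 12.9 points (Wald) v 12.7 to 12.9 (CMH), and for DCR 22.6 v 21.7 to 22.3. Coverage of both intervals is about 94% to 96%.

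**4. Size of the BOR restriction.** The same assumed responders, 30/200 and 8/100, with the unassessed share also assumed:

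| Unassessed (active / control) | CR+PR in BOR table | ORR on mITT |
|---|---|---|
| none | 15.0% v 8.0% | 15.0% v 8.0% |
| 5% / 5% | 30/190 = 15.8% v 8/95 = 8.4% | 15.0% v 8.0% |
| 10% / 10% | 30/180 = 16.7% v 8/90 = 8.9% | 15.0% v 8.0% |
| 5% / 15% | 30/190 = 15.8% v 8/85 = 9.4% | 15.0% v 8.0% |

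**The case against.** The strongest reply is that little turns on this. ORR and DCR sit behind PFS and OS in the testing order, the DMC had already recommended stopping for futility (SAP 3.5), and the two intervals perform almost alike. The SAP never uses the word unstratified, and Wald names a form of interval that a stratified estimate can also take. SAP 3.1 allows a table to state its own denominator, as the BOR table does.

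Most of this stands as a limit on severity. It does not make section 3.7 true: the SAP omits a method the protocol names, and a base that differs from protocol 8.3 is still a change when it is openly stated.

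A reader might go further and infer that the ORR denominator is undefined, so that ORR itself could leave mITT. SAP 2.2, 3.1, 3.2.3 and 5.3.1, read together, fix it as the analysis set.

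A reader might also infer that only the assessment requirement removes subjects from the BOR table, because measurable disease is inclusion criterion 3c. That is not established. SAP 4.4 summarises measurable-disease status as a variable, and the PFS rules in SAP 5.1.1 provide for a non-CR/non-PD response, so the measurable-disease condition may exclude some subjects too.

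**Conclusion.** The point holds as an undeclared departure of minor numerical size. The SAP replaces the CMH-adjusted ORR and DCR differences, narrows the BOR table, and states in section 3.7 that nothing in efficacy changed. The mismatch rests on the texts alone. Its size, about 0.1 to 0.6 points on average for the method, rests on assumed rates, strata, block size and analysed numbers; the BOR figures rest on assumed shares of unassessed subjects.

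Two larger claims are not supported. A layout with strata badly imbalanced between arms can move the example from 7.0% to 4.8%, but that layout was constructed for illustration, and stratified randomisation makes it a poor guide. Nor do the documents show that the change was driven by results. This SAP release reports the futility recommendation, but the documents give no ORR or DCR result and no reason for the change. The futility conclusion is unaffected.

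**What to change.** 1. **SAP 5.3.1.2 and 5.3.1.3:** restore the CMH-weighted stratified difference and 95% CI, using the planned randomisation strata and all mITT subjects. A Wald interval may stay as supportive. Add no rule that drops small cells. The sparse-stratum rule in SAP 5.1.1 should not be carried over cell by cell: its example counts a factor level, not a cross-classified cell. In the simulation at N = 150, about 70% of trials had a cell with fewer than 5 subjects in an arm, but none had a factor level that small. Dropping such cells would lose about 8% of subjects, while CMH coverage without any rule was already about 94.7%.
2. **SAP 5.3.1.1:** base the BOR table on all mITT subjects, showing those without an evaluable post-baseline assessment as NE and counting them as non-responders, so that CR plus PR equals ORR.
3. **Otherwise, SAP 3.7:** list the Wald method and the BOR restriction as changes, each with its reason.

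The cost is SAP wording and standard code, with no new data. BOR percentages fall slightly where subjects were excluded; per-arm ORR and DCR do not change.

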5.3.1.4. Duration of Response

DOR will be only calculated for subjects who have a confirmed response of CR or PR by independent radiology reviews.

DOR is calculated as the earliest documented date of CR or PR to the first date of documented PD or death due to any cause. For subjects without PD or death will be censored at the date of the last evaluable response assessment date. The same censoring rules outlined in Table 3 will be applied to DOR with date of randomization date replaced with the date of first response.

KM estimates (25th, 50th, 75th percentile of DOR along with the 95% CI) will be provided by the treatment group.

5.3.2. Subgroup Analyses for ORR, DCR and DOR

The secondary endpoint will be evaluated for the following subgroups.

- By histological tumor type (uterine and non-uterine) for the mITT population
- Baseline ECOG PS score (0 and 1) for the mITT population
- Prior lines of therapy (1 and >1) for the mITT population
- Prior lines of therapy (4 or more) for the non-mITT population
- Histologic tumor type in combination with number of prior lines of therapy (uterine with 1 prior line; uterine with 2-3 prior lines, non-uterine with 1 prior line; non-uterine with 2-3 prior lines) for the mITT population

6. SAFETY ANALYSES

Safety analyses will be based on safety analysis set unless otherwise specified. subjects in the safety analysis set will be analyzed according to the treatment (actually) received.

6.1. Adverse Events

The adverse event (AE) verbatim descriptions (investigator terms from the eCRF) will be classified into medical terminology using MedDRA. AEs will be coded by SOC and PT using MedDRA, Version 25.0 or later.

An AE will be defined as treatment emergent if one of the following criteria is met:

- A new AE has an onset date on or after the date that study drug (unesbulin/placebo or DTIC) is first administered up-through 30 days after the last dose of study drug.
- A pre-existing AE worsens in severity on or after the date that study drug is first administered through 30 days after the last dose of study drug.

Only treatment-emergent adverse events (TEAEs) will be included in the summary tables.

AEs with missing or partial onset date, such that it cannot be determined if the event occurred prior to the first dose of study, will be counted as TEAE.

Overall summary of TEAE table, will include number and percentage of subjects with any TEAEs, serious AEs, non-serious adverse events (non-SAEs), unesbulin/placebo-related TEAEs, DTIC-related TEAEs, TEAEs leading to unesbulin/placebo withdrawn, TEAEs leading to DTIC withdrawn and TEAEs by highest severity, will be provided by treatment group and overall.

All TEAEs will be summarized by MedDRA SOC and PT. If a subject experiences multiple AEs under the same SOC, the subject will be only counted once for the SOC with the greatest severity. Similarly, if a subject experiences multiple AEs under the same PT and SOC, the subject will be counted only once for the PT with the greatest severity. The table will be sorted by the descending order of the frequency of SOC then by the descending order of the frequency of PT under SOC based on the overall column.

In addition, the following summary tables will be provided:

- All TEAE by PT
- SAE by SOC and PT
- Non-SAE by PT
- SAE and non-SAE occurrence of each PT
- Non-SAE: subjects and occurrence for each PT by reporting threshold 5%
- Unesbulin/placebo-related TEAE by SOC and PT
- DTIC-related TEAE by SOC and PT
- TEAE leading to treatment (unesbulin/placebo or DTIC) discontinuation by SOC and PT
- TEAE leading to study discontinuation by SOC and PT

- All TEAE by maximum severity under each SOC and PT
- All TEAE with at least one Grade 3 or higher by PT

All TEAEs will be listed. In addition, subjects with death, SAE, or AE leading to discontinuation of study treatment during the study will be presented in three separate listings.

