One treatment cycle will constitute 21 days. DTIC will be administered on Day 1 of each 3-week treatment cycle. Unesbulin or placebo tablets will be administered on Days 2 and 5 of Week 1 and Days 1 and 4 of Weeks 2 and 3 of each 3-week treatment cycle (Note: the preferable duration between 2 doses of unesbulin/placebo is approximately 72 hours). Based on the results from a food effect assessment in the ongoing Phase 1b Study PTC596-ONC-007-LMS, it is recommended that unesbulin/placebo be administered with food.

All subjects will receive treatment until evidence of disease progression, unacceptable toxicity, or other withdrawal criteria are met. No crossover will be permitted.

Subjects will undergo weekly assessments throughout the study. The schedule of all study efficacy, safety, PK, and laboratory assessments is shown in Table 1, including a window for completion of the activities associated with each visit. Of note, activities designed to be completed in a single day, for example, PK sampling from before dosing to 8 hours postdose, may not be split up between the 2 days of a window.

An end-of-treatment (EOT) assessment should be performed within 30 days after the end of treatment or until recovery from or stabilization of the AE, whichever occurs latest. For subjects requiring immediate initiation of a new treatment option, the EOT visit may be completed earlier. The EOT assessments are outlined in Table 1. A safety follow-up assessment should be performed by telephone call approximately 30 days (\pm 3 days) after the EOT to assess AEs and concomitant medications. Survival follow-up (sFUP) assessments should be performed by phone every 3 months (\pm 7 days) after the EOT until the later of 184 events or 2 years after the last subject is randomized.

PK Assessment

Approximately 12 randomized subjects will participate in a PK substudy at selected sites. These subjects will be assessed for PK of unesbulin, DTIC, and AIC. The target is for approximately 7 PK evaluable subjects in the unesbulin group to complete Cycle 3.

For the DTIC/AIC PK assessment, blood samples will be collected following an intensive schedule at predose and up to 24 hours postdose on Day 1 of Cycles 1 and 3. Sparse blood samples will be collected at predose and 1.25 and 4 hours postdose (start of infusion) on Day 1 of Cycles 2 and 4.

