8.2. Sample Size Determination

The sample size for the primary analysis was computed based on the comparison of PFS between subjects randomized to unesbulin plus DTIC and subjects randomized to placebo plus DTIC. The median PFS was assumed to be approximately 1.5 to 2.5 months for the placebo plus DTIC group and more than 4 months for the unesbulin plus DTIC group. With an overall one-sided alpha level of 0.025, a total of 245 events are required to achieve at least 90% power at a hazard ratio of 0.5. Assuming 19 months of enrollment time, a minimum follow-up period of 6 months for the primary endpoint, and approximately 11.5% uniform dropout rate, a total of 300 subjects are planned to be randomized.

One interim analysis will be performed when approximately 36% of the PFS events occur (approximately 88 events). The study may stop for both efficacy and futility. The study may stop for efficacy if the observed hazard ratio is less than 0.447, and the study may stop for futility if the observed hazard ratio is more than 0.67.

The alpha allocation will be controlled separately at the interim and the final analysis timepoints by using the Lan-DeMets spending function that approximates the O'Brien-Fleming approach. The family-wise significance level is 0.025, with 0.000184 allocated at the interim analysis and 0.024816 at the final analysis.

For the key secondary endpoint OS, sample size is based on detecting a hazard ratio of 0.625 (median OS of 10 months versus 16 months, for placebo plus DTIC vs unesbulin plus DTIC, respectively) and a minimum 15-month follow-up. With 184 events (among 265 subjects) a 1-sided 0.025 level log-rank test will have approximately 84% power.

A separate group sequential design and monitoring will be performed for OS, with one interim analysis performed when at least 60% of the OS events occur and a final OS analysis when 184 events occur. The alpha allocation will be controlled by using the Lan-DeMets spending function that approximates the O'Brien-Fleming approach.

Data from the additional 45 subjects enrolled with at least 4 prior lines of therapy will not be included in the primary analysis; rather, the efficacy analysis of data from these subjects will be considered exploratory and included as a sensitivity analysis only.

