8.4.5.1. Adverse Events

AEs will be tabulated using the MedDRA classification system. The frequency of subjects experiencing a specific AE will be tabulated by treatment group, system organ class, preferred term, seriousness (nonserious versus serious), worst severity, outcome, and relationship to study drug. Subject with AEs leading to death or to discontinuation from treatment, and SAEs will be listed.

An AE will be defined as treatment emergent if one of the following criteria is met:

- A new AE has an onset date on or after the date that study drug (unesbulin/placebo or DTIC) is first administered through 30 days after the last dose of study drug.
- A preexisting AE worsens in severity on or after the date that study drug is first administered through 30 days after the last dose of study drug.

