3. GENERAL CONSIDERATIONS

3.1. General Considerations

Continuous data will be summarized using number of observations (n), arithmetic mean (mean), standard deviation, median, minimum value (min) and maximum value (max) by treatment group. Categorical variables will be summarized using the frequency count (n) and percentage (%) by treatment group. An overall/total group (i.e., sum of all treatment groups) will generally be presented additionally for summaries of disposition, demography, and baseline characteristics.

For all percentage calculations, the denominator will be the number of subjects in the analysis set for the treatment group, unless otherwise stated.

Only data from protocol scheduled visits will be included in the summary tables. Data from unscheduled visits will not be included in the summary tables but will be included in the by-subject listings. Descriptive summaries by visit and treatment will be provided for all the primary and secondary efficacy endpoints.

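### SAP 6.1 compares adverse events between arms with no measure adjusted for time at risk, so a difference in time on treatment would distort the comparison for events with continuing risk

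*SAP*

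**What the plan says.** Comparing safety and tolerability between the two arms is a secondary objective (Protocol 2.2; SAP Table 1), so the adverse event tables have to carry a between-arm comparison.

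- **How long subjects are treated.** Protocol 3.1: "All subjects will receive treatment until evidence of disease progression, unacceptable toxicity, or other withdrawal criteria are met".
- **How long events are counted.** Protocol 8.4.5.1 defines a treatment-emergent event by its onset, with the 30 days running from the final dose: "A new AE has an onset date on or after the date that study drug (unesbulin/placebo or DTIC) is first administered through 30 days after". SAP 6.1 uses the same limit, and adds: "Only treatment-emergent adverse events (TEAEs) will be included in the summary tables".
- **What is tabulated.** The headline table is specified as "Overall summary of TEAE table, will include number and percentage of subjects with any TEAEs, serious AEs, non-serious adverse events (non-SAEs", and so on. In the tables by preferred term, "the subject will be counted only once for the PT with the greatest severity". Two further tables report numbers of occurrences by preferred term.
- **The denominator.** SAP 3.1: "the denominator will be the number of subjects in the analysis set for the treatment group, unless otherwise stated". Nothing in SAP 6.1 states otherwise.
- **Exposure.** SAP 4.8 derives and summarises duration of exposure by arm, but neither document links it to adverse events.
- **The interim result.** SAP 3.5 gives the futility bound as an observed PFS hazard ratio above 0.67 at 88 events. It records that the DMC recommended discontinuing the study for futility.

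**The concern.** Because treatment continues to progression, the period over which a subject can contribute an event depends on the efficacy outcome and on early withdrawal. A subject treated longer is watched longer. A percentage of subjects with an event then mixes the rate at which the drug causes events with the time over which they could be seen. Occurrence counts mix the two in the same way, because they are not divided by time either.

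The distortion can run in either direction. If unesbulin delays progression, its arm can show more events at the same underlying rate. If more subjects stop unesbulin early, for example for intolerable toxicity, its counting window shortens and the crude percentages understate its harm. A separate exposure table tells the reader that the windows differ, but does not let the reader correct the incidence of a given preferred term.

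**Working it through.** The documents give no adverse event rate, no exposure by arm and no safety precision figure, so there is no planned number to reproduce. The check asks how large a difference would appear if the two arms had exactly the same event rate.

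**Inputs from the documents.** Protocol 8.2: "The median PFS was assumed to be approximately 1.5 to 2.5 months for the placebo plus DTIC group and more than 4 months" in the other arm, with a design hazard ratio of 0.5; I take a 2-month control median from within that range. Futility bound 0.67 (SAP 3.5). Counting extension 30 days, w = 30/30.44 = 0.986 months.

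**Assumptions.** Time on treatment is exponential and ends at progression. The first-event rate h is constant and equal in both arms, 0.1 per month, with 0.05 to 0.5 as the range.

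**Formula.** With L = ln 2 / median PFS, the crude proportion of subjects with an event is

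P = 1 − exp(−h·w) × L/(L + h).

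Control arm: L = 0.693/2 = 0.347, and exp(−0.1 × 0.986) = 0.906, so P = 1 − 0.906 × 0.347/0.447 = 29.7%. For the unesbulin arm, L is multiplied by the hazard ratio (differences are from unrounded values):

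| Hazard ratio | L (unesbulin) | Crude %, unesbulin | Crude %, placebo | False difference, points |
|---|---|---|---|---|
| 0.5 (design) | 0.173 | 42.5 | 29.7 | 12.9 |
| 0.67 (futility bound) | 0.232 | 36.7 | 29.7 | 7.0 |
| 0.8 | 0.277 | 33.4 | 29.7 | 3.7 |
| 0.9 | 0.312 | 31.4 | 29.7 | 1.7 |
| 1.0 | 0.347 | 29.7 | 29.7 | 0 |

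**Other event rates.** At 0.05, 0.2 and 0.5 per month the false difference is 4.9, 8.0 and 5.6 points at hazard ratio 0.67, and 2.5, 4.4 and 3.2 points at 0.8.

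**Reversed direction.** Read the 0.8 row the other way. If unesbulin were the arm with the 2-month median time on treatment and placebo had 2.5 months, the same event rate would show 29.7% against 33.4%, which is 3.7 points in unesbulin's favour.

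**Early-onset events.** Suppose the risk exists only in the first 6 weeks (1.38 months). Then P is the average of 1 − exp(−h × min(1.38, T + w)) over the treatment time T. At h = 0.1 and medians of 2 against 4 months this gives 12.7% against 12.8%. Almost no bias remains, even at the design hazard ratio.

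**Does dividing by time at risk repair it?** In simulated data with medians of 2 and 4 months, subjects with a first event per unit of time at risk gave 0.101 and 0.100 per month when the true rate was 0.1, and 0.200 and 0.200 when it was 0.2. Crude percentages from the same data were 29.8% against 42.5%, and 48.0% against 62.0%.

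**The case against.** The strongest case against is that this matters little here.

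1. *The study met futility.* This stands. A reader might infer from the design assumptions that a false excess of about 13 points is to be expected. The documents do not support that: it needs the design hazard ratio of 0.5, and the SAP that contains the tables already records the futility recommendation. The relevant range starts near 7 points and falls to zero. The point does not vanish, however. The observed hazard ratio and exposure by arm are not in the documents, and similar PFS does not guarantee similar time on treatment, since subjects also leave for toxicity.
2. *The plan is not confined to crude percentages.* Correct. A reader of the headline table might infer that it is, but SAP 6.1 also lists occurrence counts and SAP 4.8 reports exposure. Neither adjusts for time at risk.
3. *Safety is judged on more than adverse events.* Correct. A reader might infer that the safety objective cannot be answered at all. That goes too far: SAP 6.2, 6.3 and 6.5 summarise laboratory values, vital signs and QTc by visit or time point and by arm. Protocol 1.3 says the most common treatment-related Grade 3 or 4 events in the Phase 1b study were associated with myelosuppression, which the laboratory summaries would pick up.
4. *A constant rate is doubtful.* It stands as a limit on the size. Events concentrated early show almost no bias, and very common events are near saturation: at 0.5 per month the ratio of percentages is 1.12 at hazard ratio 0.5 and 1.08 at 0.67.
5. *The tables are descriptive.* No between-arm test of adverse events is planned, but readers will still compare the two columns. The table shells are in a separate document that could not be checked; the tables SAP 6.1 itself lists include none adjusted for exposure.

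**Conclusion.** The point holds in a limited form. No adverse event table in SAP 6.1 is adjusted for time at risk or restricted to a common window, although the counting window depends on how long each subject stays on treatment. If time on treatment differs, the tables overstate continuing-risk events in the longer-treated arm and understate toxicity in an arm that stops early.

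Under an equal constant rate of 0.1 per month, a 2-month control median and treatment ending at progression, the artefact is about 7 points at hazard ratio 0.67, about 4 at 0.8 and none at 1.0; it would be 13 at the design value. PFS stands in for time on treatment, which other discontinuations would shorten. Whether the artefact is present in this trial, and in which direction, cannot be told from the documents. This is a worthwhile, inexpensive improvement rather than an error that invalidates the safety analysis.

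**What to change.** Keep the crude tables in SAP 6.1 and add beside them:

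- **Exposure-adjusted incidence rates:** subjects with a first event per 100 subject-months at risk, from first dose to the earlier of first event or last dose + 30 days, with the arm difference and 95% CI. Report these for any TEAE, Grade 3 or higher TEAEs, SAEs, TEAEs leading to discontinuation of unesbulin/placebo or of DTIC, and the most frequent preferred terms. Take the last dose as in the TEAE definition, and end time at risk at death or data cut-off if earlier.
- **Crude incidence restricted to Cycles 1-2** (the first 6 weeks), by arm. The first scheduled on-treatment scan falls at about 6 weeks, so few subjects should have left for radiological progression before then.

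State that between-arm differences in adverse events will be interpreted with these alongside the crude percentages.

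The cost is a few extra tables from event and dose dates already needed for the planned ones; SAP 4.8 already derives exposure. The rates assume a roughly constant hazard over time at risk, and the Cycles 1-2 table offsets that for early events. Nothing in trial conduct changes.
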